### 3.6 Pharmacokinetic Analysis

The plasma pharmacokinetics of ISIS 757456 (as total full-length oligonucleotides or ISIS 757456-equivalent, ISIS 757456-eq.) will be assessed following SC administration(s). PK analysis summary will be based on PK set.

Metabolite identification and profiling may be determined in some of the collected plasma samples and will be reported separately.

#### 3.6.1 Plasma Concentration Data of Total Full-Length Oligonucleotides

Plasma concentrations of ISIS 757456 (ISIS 757456eq.), along with the scheduled (nominal) and actual samples times (i.e., time from SC dosing) will be listed (when applicable) for each patient, by treatment group, nominal dose, and day. In addition, percent differences between scheduled and actual sampling times will also be listed for all patients. Percent differences between actual administered dose and nominal dose will also be listed.

Plasma concentrations below the lower limit of quantification (LLOQ) will be indicated by "BLQ". For the purpose of calculating typical descriptive statistics (n, mean, SD, %CV, geometric mean, geometric %CV, median, minimum, and maximum) for plasma concentrations, all BLQ values will be set to zero. Mean plasma concentrations that are BLQ will be presented as "BLQ", and the SD and %CV will be reported as not applicable. Summary statistics of the ISIS 757456 plasma concentrations will be tabulated by treatment group, nominal dose, day, and scheduled time point. At the discretion of the pharmacokineticist and/or biostatistician, samples may be excluded from descriptive statistics if there are large deviations between scheduled and actual sampling times, or large deviations between actual dose and nominal dose.

ISIS 757456eq. plasma concentration versus time (actual) profiles for each patient that received ISIS 757456 active treatment, as well as the mean ( $\pm$  SD or SE) plasma concentrations versus time (scheduled) profiles, will be presented graphically on linear and semilogarithmic scales. At the discretion of the pharmacokineticist and/or biostatistician, samples may be excluded from the mean plots if there are large deviations between scheduled and actual sampling times.

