### **3.4.3. Post-Treatment**

Subjects are to return to the Study Center for Post-Treatment visits on Study Days 57, 64, 78, 92, 120, and 141. The final study visit will be Study Day 141 (Study Week 21).

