#### 3.6.2 Plasma Pharmacokinetic Parameters

The plasma PK of ISIS 757456 (as total full-length oligonucleotides) will be assessed following the SC administration. Non-compartmental PK analysis of ISIS 757456 (total full-length oligonucleotides) will be carried out on each individual subject data set using Phoenix WinNonlin version 8.0 or higher (Pharsight Corporation, Mountain View, CA). For calculation of PK parameters, all BLQ values will be set to zero. The plasma PK parameters for ISIS 757456eq. will be calculated based on actual sampling times. Since only trough and post-treatment follow up PK samples are to be collected, only the following PK parameters will be calculated:

- $C_{\text{trough}}$
- $t_{1/2\lambda z}$

Other plasma PK parameters, as appropriate, may be determined or calculated at the discretion of the PK scientist.

Plasma pharmacokinetic parameters will be summarized using descriptive statistics (n, mean, SD, %CV, geometric mean, geometric %CV, median, minimum, and maximum) by treatment group, nominal dose, and day.

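### SAP 3.6.1 and 3.6.2 set BLQ concentrations to zero but request geometric statistics, which become zero or undefined at any post-dose visit with a BLQ value

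*Combined protocol and SAP*

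**What the plan says.** SAP 3.6.1 gives one rule for a whole list of concentration statistics, and the list names geometric mean and geometric %CV: "for plasma concentrations, all BLQ values will be set to zero".

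Two other provisions of SAP 3.6.1 bear on the point:
- A display rule: "Mean plasma concentrations that are BLQ will be presented as 'BLQ', and the SD and %CV will be reported as not applicable".
- A discretionary exclusion: "samples may be excluded from descriptive statistics if there are large deviations between scheduled and actual sampling times". It also covers large differences between actual and nominal dose.

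SAP 3.6.2 repeats the zero rule: "For calculation of PK parameters, all BLQ values will be set to zero". It limits the parameters to Ctrough and terminal half-life: "Since only trough and post-treatment follow up PK samples are to be collected, only the following PK parameters will be calculated". It then asks for geometric statistics of those parameters: "Plasma pharmacokinetic parameters will be summarized using descriptive statistics (n, mean, SD, %CV, geometric mean, geometric %CV". SAP 3.2.1 also lists the geometric mean for PK parameters.

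Protocol Appendix C schedules one PK sample per visit. Day 1 is pre-dose. Days 3 to 50 are pre-dose troughs. The remaining samples are taken at the "Post-Treatment visits on Study Days 57, 64, 78, 92, 120, and 141" (protocol 3.4.3). Neither document states the lower limit of quantification (LLOQ).

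**The concern.** The zero rule suits arithmetic means and is a common convention for them. Applied to geometric statistics it conflicts with the request made in the same sentence, because a single zero overrides every other value in a product and cannot be logged. A programmer who follows the text prints a geometric mean of zero beside an arithmetic mean well above the LLOQ, with an empty geometric %CV. A programmer who departs from the text has to choose a replacement rule after seeing the data. Trough and post-treatment samples are the only PK data this trial collects, so these tables are its whole summary of exposure. SAP Section 1 says the plan exists to give specific guidelines and that deviations will be documented in the study report. Here the stated rule cannot sensibly be followed.

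**Working it through.** **Inputs.** About 30 subjects randomized 2:1 (SAP 3.1) give 30 × 2/3 = 20 active subjects. The SAP's PK Set contains only subjects dosed with ISIS 757456 (SAP 3.2.2). The documents state no figure on this point, so there is none to reproduce.

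**Formulas.**
- Geometric mean = exp(mean of log x) = (product of x)^(1/n).
- Geometric %CV = 100 × √(exp(variance of log x) − 1).
- With any x = 0, the product is 0, log x is minus infinity, and the variance of log x is undefined.

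**Illustration.** These are simulated values, not trial data: 20 log-normal concentrations with median parameter 10 and log-scale SD 0.5. In all rows but the first, the lowest value is made BLQ.

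| Handling | Geometric mean | Geometric %CV |
|---|---|---|
| All 20 quantifiable | 10.19 | 30.3% |
| One BLQ set to 0 (SAP rule) | 0 | undefined |
| Quantifiable values only (n = 19) | 10.56 | 26.2% |
| BLQ = LLOQ/2, LLOQ assumed 0.5 | 8.75 | 107% |
| BLQ = LLOQ/2, LLOQ assumed 1 | 9.06 | 83% |
| BLQ = LLOQ/2, LLOQ assumed 2 | 9.38 | 64% |

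Under the SAP rule the arithmetic mean moves only from 10.60 to 10.34 and the SD from 2.91 to 3.58. The median stays at 10.89. The damage is confined to the geometric statistics. The rule that replaces zero matters, mainly for the %CV, so it should be fixed in advance.

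**Does the display rule help?** It is triggered when the mean is BLQ. With k zeros among 20, the mean is below the LLOQ only if the quantifiable values average less than 20/(20 − k) × LLOQ. For k = 1 that is 20/19 = 1.05 × LLOQ; for k = 10 it is 2 × LLOQ. A visit with a few BLQ values among clearly quantifiable ones does not trigger it. In the illustration the mean of 10.34 is far above every LLOQ assumed. When the rule is triggered, it names SD and %CV, not the geometric statistics.

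**How often?** With per-sample BLQ probability p, assumed independent across subjects, the chance of at least one BLQ among 20 is 1 − (1 − p)^20.

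| Assumed p | Chance that a visit is affected |
|---|---|
| 1% | 18% |
| 5% | 64% |
| 10% | 88% |
| 20% | 99% |

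The documents do not say which p applies. Sampling runs to Day 141, which is 91 days after the last scheduled dose on Day 50, so late BLQ values are plausible but not certain.

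**Half-life.** Half-life = ln 2 / λz, where −λz is the slope of log concentration on time within one subject. A zero cannot enter that regression. The six post-treatment samples fall 7, 14, 28, 42, 70 and 91 days after Day 50. With noise-free exponential decline and an assumed half-life of 14, 21 or 28 days, making the last 1, 2 or 3 samples BLQ and leaving them out keeps 5, 4 or 3 points, and the fit returns the assumed value each time. Trailing BLQ values therefore cost points and precision, but do not make the half-life zero or undefined.

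**The case against.** **The display rule could be read generously.** A geometric mean of zero is a mean below the LLOQ, so it might be shown as BLQ. That reading is open, although the text does not name geometric statistics. It would replace a false zero with an uninformative entry: one BLQ subject would hide the geometric mean of 19 quantifiable ones, and the geometric %CV would still have no rule.

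**The consequence is small.** This stands. Arithmetic mean, SD, median, minimum and maximum stay defined, and SAP 3.6.1 lists each subject's concentrations with BLQ marked. Protocol 10.6.4 asks only that concentrations be listed and summarized descriptively. The exposure-response work in SAP 3.6.3 relates Ctrough to response and does not call for geometric means.

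**The size cannot be known.** This also stands. With no LLOQ and no expected concentrations, it is possible that no post-dose visit is affected.

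**Stronger readings that a reader might infer:**
- *That half-life fails wherever a value is BLQ.* The documents do not support this. Half-life is fitted within a subject to the quantifiable terminal samples; Day 1 plays no part; calculated half-lives are positive, so their geometric summaries across subjects are defined. What remains is that SAP 3.6.2, read literally, puts zeros into a log-linear fit and does not say they are left out.
- *That the Day 1 table will be wrong for every subject.* That sample precedes any drug, so BLQ is the expected result, and the display rule largely covers a visit where all values are BLQ.

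**Conclusion.** The point holds for the geometric mean and geometric %CV of plasma concentrations (SAP 3.6.1) and of Ctrough (SAP 3.6.2). At a post-dose visit with at least one BLQ value, the stated rule makes the first 0 or not computable and the second undefined. This is algebra and rests on no assumption about the data. No other provision repairs it: the display rule depends on a BLQ mean and omits the geometric statistics, and the discretionary exclusion concerns timing and dose deviations, not BLQ results.

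The number of visits affected is unknown; the 18% to 99% range rests on assumed BLQ rates of 1% to 20%, independence between subjects and 20 active subjects. For half-life, the only gap is a missing statement that BLQ values are left out of the regression. The issue is minor. It touches descriptive PK tables only and leaves the primary and secondary AGT analyses unchanged.

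**What to change.** In SAP 3.6.1, and for Ctrough in SAP 3.6.2:
- Keep BLQ = 0 for the arithmetic statistics.
- Compute geometric mean and geometric %CV by one named rule, for example quantifiable values only.
- Print the number quantifiable and the number BLQ beside them.
- When the mean is BLQ, show the geometric mean as BLQ and the geometric %CV as not applicable.

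In SAP 3.6.2, state that BLQ values are excluded from the terminal log-linear regression rather than set to zero. A minimum number of quantifiable points could be named in the same sentence.

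The cost is a few sentences and two count rows in the PK tables, with no new data. There are two small downsides. Geometric and arithmetic rows may rest on different numbers of subjects, which the counts make visible. Using quantifiable values only also pushes the geometric mean up somewhat: in the illustration 10.56 against 10.19, a ratio of 1.04. The shift grows as more values are BLQ, which is a further reason to print the counts.

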#### 3.6.2 Plasma Pharmacokinetic Parameters

The plasma PK of ISIS 757456 (as total full-length oligonucleotides) will be assessed following the SC administration. Non-compartmental PK analysis of ISIS 757456 (total full-length oligonucleotides) will be carried out on each individual subject data set using Phoenix WinNonlin version 8.0 or higher (Pharsight Corporation, Mountain View, CA). For calculation of PK parameters, all BLQ values will be set to zero. The plasma PK parameters for ISIS 757456eq. will be calculated based on actual sampling times. Since only trough and post-treatment follow up PK samples are to be collected, only the following PK parameters will be calculated:

- $C_{\text{trough}}$
- $t_{1/2\lambda z}$

Other plasma PK parameters, as appropriate, may be determined or calculated at the discretion of the PK scientist.

Plasma pharmacokinetic parameters will be summarized using descriptive statistics (n, mean, SD, %CV, geometric mean, geometric %CV, median, minimum, and maximum) by treatment group, nominal dose, and day.

### 3.6.3 Pharmacokinetic/Pharmacodynamic Exposure-Response Analysis

Exposure-response correlations may be explored graphically between plasma exposure (e.g.  $C_{trough}$ ), and selected PD measures (e.g. serum AGT level), other relevant biomarkers (such as plasma renin activity, angiotensin II, etc.) and relevant clinical endpoints (such as in-clinic systolic blood pressure). In addition, the relationship between serum AGT level with plasma concentrations ( $C_{trough}$ ) of ISIS 757456 eq. may be further evaluated with an inhibitory effect  $E_{max}$  model.

Population PK and PKPD analysis may be performed using the PK and PD data from this Study, and/or combined with other ISIS 757456 clinical PK/PD data from any previous and future studies in the development timeline.

### 3.6.4 Immunogenicity (IM) Analysis

The samples for immunogenicity are not planned to be analyzed.

## 3.7 Safety Analyses

The safety analysis will be conducted on the Safety Set.

### 3.7.1 Exposure

Treatment duration and amount of Study Drug (ISIS 757456 or placebo) received will be summarized by treatment group. The treatment duration for each subject is defined as last dose date - first dose date +1.

### 3.7.2 Adverse Events

The incidence of adverse events (AEs) will be summarized by Medical Dictionary for Regulatory Activities (MedDRA) version 22.0 (or higher) preferred term and system organ class for:

- Any treatment emergent adverse events (TEAEs).
- Related TEAEs. Related is defined as "Related", "Possible", or missing relationship to study drug.
- Any TEAEs by severity. At each severity level of subject summarization, a subject is classified according to the highest severity if the subject reported one or more events. AEs with missing severity will be categorized as "Missing" for this summary.
- Serious TEAEs (Treatment-emergent SAEs).
- TEAEs leading to permanent study drug discontinuation.

Serious and non-serious AEs that lead to study discontinuation or investigational drug discontinuation will be listed separately. Non-treatment emergent adverse event will be included and be noted in the subject AE listing.

To determine the AE as treatment-emergent or not, if there is no "Formlink" link, and the AE (start date/time) occurs after the subject's first dosing date/time, then the AE is treatment-emergent. Otherwise, if the AE (start date/time) occurs prior to the subject's first dosing date/time, then the AE is not treatment-emergent.

In addition, if there is a "Formlink" link between two AE records, then we compare them pairwise, and consider two cases, where we compare the AE severity (mild/moderate/severe) and seriousness (Yes/No) between the two records in the pair. We chronologically order the 2 records (by AE start date) and refer to the "first" and "second" AE.

Case 1: The first AE record in the pair occurs before first dosing, and the second AE record occurs after first dosing.

If the AE severity or seriousness of the second record is worse than that of the first record, then only the second AE is deemed as a TEAE. Otherwise, neither record is considered as TEAE.

Case 2: Both AE records in the pair occur after first dosing.

If the AE severity or seriousness of the second record is worse than that of the first record, then two TEAEs are recorded. Otherwise only the first AE record is deemed as a TEAE.

All TEAEs identified based on the rules above will be summarized in the event number analysis.

The most conservative approach will be used to determine if the event occurs after the treatment. For example, if the onset date or resolution date of an AE is prior to the first study treatment date, it will be considered to have occurred prior to the study period. If the onset or resolution date of an AE is a partial date with only month or year available or complete missing, then the event is assumed to be within the study period unless the year is prior to the year of the first study treatment date, or if in the same year, the month is prior to the month of the first study treatment date.

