#### 9.4.3.5. Outcome of the AE

If the event is a non-serious AE, then the event's outcome is characterized by 1 of the following:

- **AE Persists:** Subject terminates from the trial and the AE continues
- **Recovered:** Subject recovered completely from the AE
- **Became Serious:** The event became serious (the date that the event became serious should be recorded as the Resolution Date of that AE and the Onset Date of the corresponding SAE)
- **Change in Severity (if applicable):** AE severity changed

If the event is an SAE, then the event's outcome is characterized by 1 of the following:

- **Ongoing:** SAE continuing
- **Persists (as non-serious AE):** Subject has not fully recovered but the event no longer meets serious criteria and should be captured as an AE on the non-serious AE eCRF (the SAE resolution date should be entered as the date of onset of that AE)
- **Recovered:** Subject recovered completely from the SAE (the date of recovery should be entered as the SAE resolution date)
- **Recovered with Sequelae:** The signs/symptoms of the reported SAE have improved but not completely resolved, and a new baseline for the subject is established since full recovery is not expected
- **Fatal:** Subject died (the date of death should be entered as the SAE resolution date)
- **Unknown:** The outcome of the reported SAE is not available, e.g., subject is lost to follow-up

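### The SAP's incomplete-date rule for adverse events is triggered by a missing resolution date as well as a missing onset, with no order of precedence, so some AEs known to be pre-dose are classed two ways

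*Combined protocol and SAP*

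**What the plan says.** SAP 3.7.2 contains three statements that bear on whether an AE counts as treatment-emergent.

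- **Start-date rule**, for AEs without a link to another AE record: "if the AE (start date/time) occurs prior to the subject's first dosing date/time, then the AE is not treatment-emergent". A start after first dosing makes the AE treatment-emergent. The resolution date plays no part.
- **Known pre-dose date**, in the later paragraph on dates, with the study period as its reference point. It covers an event whose "onset date or resolution date of an AE is prior to the first study treatment date, it will be considered to have occurred prior".
- **Incomplete date**, the next sentence. Its trigger is "If the onset or resolution date of an AE is a partial date with only month or year available or complete missing". The default that follows from the trigger places the event inside the study period. An exception applies when the year, or the month within the same year, precedes that of first treatment. The sentence does not say whether this is the year and month of onset or of resolution.

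The date paragraph gives its own purpose: "The most conservative approach will be used to determine if the event occurs after the treatment".

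Protocol 9.4.3.5 provides an outcome for non-serious AEs that are still open at study exit ("Subject terminates from the trial and the AE continues") and assigns it no resolution date. Under protocol 9.4.2, AE recording starts once consent is signed. Under protocol 3.4.1, screening lasts up to 28 days. AEs with pre-dose onset can therefore be in the database.

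**The concern.** Both sentences of the date paragraph are triggered by either date, so one record can satisfy both and get opposite answers. An ongoing AE has no resolution date, so it meets the incomplete-date trigger even when its onset is known to the day. An AE known to have ended before the first injection meets it when its onset is incomplete. In both situations the timing relative to first dose is already settled by a known date, so the appeal to conservatism is not needed and does not say which sentence wins.

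Incidence and severity of TEAEs is the safety endpoint in both documents (protocol 1.2.4, SAP 1.3.3). Two programmers working faithfully from this text could produce different TEAE flags. One version would tabulate pre-treatment events as treatment-emergent.

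**Working it through.** The plan states no figure to reproduce, so the check applies each rule to test records. Take an illustrative first dose on 15 February 2020. The exception clause is read in two ways: on the incomplete date itself, or on the onset date.

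| | Onset | Resolution | Start-date rule | Known pre-dose date | Incomplete date, exception read on the incomplete date | Incomplete date, exception read on onset |
|---|---|---|---|---|---|---|
| 1 | 5 Feb 2020 | missing | not TEAE | prior | within | within |
| 2 | 25 Jan 2020 | missing | not TEAE | prior | within | prior |
| 3 | 5 Feb 2020 | March 2020 | not TEAE | prior | within | within |
| 4 | missing | 10 Feb 2020 | cannot decide | prior | within | within |
| 5 | Feb 2020 | 10 Feb 2020 | cannot decide | prior | within | within |
| 6 | 1 Mar 2020 | missing | TEAE | not triggered | within | within |

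- Records 1 and 3 conflict under both readings. The start-date rule and the known-date sentence agree; only the incomplete-date sentence dissents.
- Record 2 conflicts only if the exception is read on the missing resolution date.
- Records 4 and 5 conflict under both readings, and also if the exception is read on the resolution date, because February does not precede February. The start-date rule has no complete date to use, so the contradiction lies wholly inside the date paragraph.
- Record 6, an ordinary ongoing post-dose AE, is not in conflict.

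**How often a pre-dose onset shares the dosing month.** Assume that first-dose dates are uniform over 2020 and onset is uniform over the 28 days before dosing. For a first dose on day *d* of a month, the number of the 28 preceding days in the same month is min(*d* − 1, 28). Summed over the days of a month:

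- 31-day month: (0 + 1 + … + 28) + 28 + 28 = 406 + 56 = 462
- 30-day month: 406 + 28 = 434
- 29-day February: 406

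Total: 7 × 462 + 4 × 434 + 406 = 3234 + 1736 + 406 = 5376 pairs, out of 366 × 28 = 10248. The share is 5376 / 10248 = 52%.

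So if the exception is read on onset, about half of ongoing AEs with a complete screening-period onset would be in conflict. If it is read on a wholly missing resolution date, all of them would be. This is a share of such AEs, not of TEAEs or of subjects.

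**Weight of one record.** About 30 subjects at 2:1 is about 20 and 10 per arm. One subject is then 1/20 = 5 percentage points on active or 1/10 = 10 points on placebo, and only if that subject has no other event in the same table row. The documents give no count of such AEs, so the calculation stops here.

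**The case against.** The strongest reply is that the start-date rule defines a TEAE and the date paragraph is only a fallback for dates that cannot be compared. The start-date and linked-record rules come first and close by saying that the TEAEs they identify are the ones summarized. For a complete pre-dose onset, two of the three statements already agree, and letting a blank resolution date override them is the least natural reading. This has real force for records 1 to 3. It does not remove the problem: the date paragraph says that it decides whether an event follows treatment, and the SAP nowhere says that the start-date rule prevails. It gives no help for records 4 and 5.

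It is also fair to say that such records should be rare. Conditions present before consent are medical history unless they worsen (protocol 9.4), AEs are collected prospectively, and edit checks and queries pursue missing data before lock (SAP 2.5.1). Randomization is on Day 1 (protocol 4.2), so a screening AE precedes assignment and misclassification is not expected to favor an arm. AEs that are not treatment-emergent are marked in the listing, so flags can be traced.

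Three stronger readings are tempting, and the documents do not support them.

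- *Every ongoing pre-dose AE is classed both ways.* Record 2 shows that this fails if the exception refers to onset.
- *TEAE rates would shift by some stated amount.* That needs a number of affected subjects, which neither document gives.
- *The related and discontinuation tables are contaminated too.* This is doubtful. A screening AE reported before dosing carries the action category for not applicable (protocol 9.4.3.3). A possible relationship requires plausible timing relative to study drug (protocol 9.4.3.1), although SAP 3.7.2 does count a missing relationship as related.

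**Conclusion.** The point holds as an internal contradiction in a stated safety rule, limited to two kinds of record:

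1. a complete pre-dose onset in the calendar month of first dose with no resolution date (or a partial later one), extending to any pre-dose month if the exception is read on the missing resolution date;
2. a missing onset, or a partial onset in the dosing month, with a known pre-dose resolution in that month.

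The first kind has a sensible answer elsewhere in SAP 3.7.2, but the SAP does not say that this answer prevails. The second has no tie-break anywhere.

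The any-TEAE and severity tables are mainly exposed. The primary AGT analysis is unaffected. The 52% calendar share rests on the uniform-date assumptions and describes only the first kind, with the exception read on onset. No effect on TEAE incidence can be estimated. The case for correcting the text is that it can produce a wrong flag and is nearly free to repair, not that a large distortion is expected.

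**What to change.** Replace the two date sentences in SAP 3.7.2 with one ordered rule:

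1. If the onset date is complete, classify by onset alone under the start-date rule and ignore a missing or partial resolution date.
2. If the onset is partial or missing and a complete resolution date lies before first dose, the AE is not treatment-emergent.
3. Otherwise, treat a partial or missing onset as treatment-emergent unless its known year, or year and month, precedes that of first dose.

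On the test records, step 1 makes 1 to 3 not treatment-emergent and 6 treatment-emergent, and step 2 makes 4 and 5 not treatment-emergent. The conservative default stays where timing is truly unknown. Limiting the trigger to onset would not be enough by itself, because records 4 and 5 would still meet both sentences.

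The cost is a few sentences in the SAP and a few lines of derivation code, with no new data. It should be settled before the TEAE flag is programmed.
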